The protocol, informed consent form(s), recruitment materials, and all participant materials will be submitted to the Institutional Review Board (IRB) for review and approval. Approval of both the protocol and the consent form must be obtained before any participant is enrolled. Any amendment to the protocol will require review and approval by the IRB before the changes are implemented to the study. In addition, all changes to the consent form will be IRB-approved; a determination will be made regarding whether a new consent needs to be obtained from participants who provided consent, using a previously approved consent form.

PROTOCOL SUMMARY

1.1 SYNOPSIS

Study Title:	DIRECTED TOPICAL DRUG DELIVERY FOR TREATMENT FOR PASC HYPOSMIA
Study Product:	Beclomethasone; Vectra F-microsponge ; PosiSep microsponge
Study Description:	This study will compare topical intranasal directed administration of a Vectra F or PosiSepmicrosponge with Beclomethasone versus placebo for the treatment of persistent olfactory loss due to COVID-19. We hypothesize that treatment with drug will result in improved olfactory function.
Objectives:	Primary Objective: To determine if directed topical drug treatment results in improved olfactory function, compared to placebo.
Endpoints:	Primary Endpoint: Olfactory function at 6 and 18 weeks post-enrollment. Secondary Endpoints: Olfactory-specific quality of life questionnaire.
Study Population:	Adult patients of either gender presenting to Duke Rhinology Clinic with hyposmia following COVID19 lasting > 3 months, documented by abnormal score on objective olfactory testing.
Phase:	2
Description of Sites/Facilities Enrolling Participants:	Duke University School of Medicine Head and Neck Surgery clinic.
Description of Study Intervention:	Subjects will be randomized to receive either Beclomethasone or placebo. Drug will be administered topically on an intranasal microsponge, placed in the olfactory cleft using a nasal endoscope, on Day 1 and repeated on day 14.
Study Duration:	12 months
Participant Duration:	4.5 Months

1.2 SCHEMA

1.3 SCHEDULE OF ACTIVITIES (SOA)

Procedures	Screening Day -2 to 0	Enrollment/Baseline Day 0	Study Visit 2 Day 14 +/-5 days	Study Visit 3 week 6 +/- 1 weeks	Study Visit 4 week 18 +/- 2 weeks
Informed consent	X				
Demographics	X				
Medical history	X				
Physical Exam	X				
Vital Signs ¹	X		X	X	X
Concomitant Medications Review	X				
SIT (olfaction test)	X			X	X
QOD (questionnaire)	X			X	X
Randomization	X				
Physical exam, with nasal endoscopy	X				
Administer study intervention		X	X		
Adverse event review and evaluation		X	X	X	X

1.4 TIME AND EVENTS KEY

1 – Vital Sign measurements that will be collected are heart rate, blood pressure, temperature, height and weight at a minimum. (**Note:** that height will only be collected at Screening.)

INTRODUCTION

1.5 STUDY RATIONALE

COVID19 is a common cause of olfactory loss. Studies indicate that objective smell loss lasting > 3 month occurs in up to 10% of subjects with Covid smell loss. There are no effective drug treatments available, although olfactory training therapy has been used for some forms of post-viral smell loss with limited benefits. Our recent research has identified evidence for ongoing local inflammatory changes in the olfactory area of the nose in long-COVID smell loss patients. Nasal spray meds, such as steroids, are known to not reach this region of the nose well. Therefore, we propose to test this simple pharmacologic intervention in long-COVID smell loss patients with objective olfactory loss, to directly deliver a topical nasal steroid to the olfactory cleft of the nose in an absorbable sponge. Both the medication and sponge are approved for use in the nose and sinuses.

1.6 BACKGROUND

Persistent anosmia (a loss of one's sense of smell) affects an estimated 14 million people in the US¹. Many persistent acquired forms of anosmia are thought to be due to neurodegenerative processes such as aging (presbyosmia) or damage to the nasal olfactory neuroepithelium (post-viral or post head trauma anosmia)². Of these conditions, post-COVID smell loss has emerged as a major problem, impacting >30 million people globally. **Currently, we have no treatments for this problem.**

The pathogenesis of post-COVID smell loss is incompletely understood. Our recent research suggests that post-COVID hyposmics harbor ongoing local inflammation in the mucosa of the olfactory cleft of the nose, accompanied by fewer intact olfactory neurons. Normally, damaged olfactory neurons are replaced by basal progenitor cells, but it is thought that inflammation impairs this recovery process. **We hypothesize that an intervention to deliver anti-inflammatory medication directly to the olfactory area of the nose would help promote olfactory recovery.**

In considering possible therapeutic approaches, direct endoscopic application of an absorbable sponge impregnated with a steroid medicine is attractive. Steroids such as beclomethasone are FDA approved for both topical nasal administration and have a long track record of safe clinical use. Also, a dissolvable drug delivery microsphere (Vectra and PosiSep) is approved for nasal or sinus application. The use of a microsphere is ideal, since the olfactory area of the nose sits superiorly and a simple liquid would drip to the nasal floor if applied directly, and a self-administered spray does not efficiently reach this region of the nose. Given the safety record of the microsphere and steroid, we propose to undertake a human study testing this therapy for treatment of post-COVID persistent hyposmia. Identification of an effective therapy for certain forms of anosmia would be a significant advance, as there currently are no treatments available.

1.7 RISK/BENEFIT ASSESSMENT

1.7.1 KNOWN POTENTIAL RISKS

Risks from medication: beclomethasone is FDA approved, with many-year safety history. It is widely used for topical nasal delivery for allergy or rhinitis. Potential risks of long-term use include elevated ocular pressure in subjects with glaucoma, or possibly localized nasal irritation. The Vectra microsphere and PosiSep microsphere is approved for nasal and sinus application. It is widely used to place into a narrow sinus drainage region after surgery to soak with steroid for local delivery, in an effort to prevent swelling or blockage. The material dissolves generally within 6-7 days. Potential risks include tissue injury during endoscopic placement, although this is unlikely when applying it to the olfactory cleft region between the middle turbinate and nasal septum.

Other risks: There is no economic risk, as we will supply the study medication. The pre-study work up and care is the standard-of-care, unchanged, and is no different for patients choosing or not choosing to participate in this study (nasal exam and psychophysical olfactory assessment using the Smell Identification Test (Sensonics). Psychologically, there is the risk of disappointment from possible lack of improvement or from treatment with placebo. However, the current standard-of-care is no treatment, so we will counsel patients regarding this.

1.7.2 KNOWN POTENTIAL BENEFITS

The immediate and long-range potential benefit is improvement in olfactory function. As stated, the standard of care for persistent post-COVID hyposmia is observation, and many patients do not recover olfaction. Translational research findings support the conclusion that effective treatment of olfactory cleft inflammation may help recovery. Thus, there is potential that olfactory neuron will improve with treatment in this study.

1.7.3 ASSESSMENT OF POTENTIAL RISKS AND BENEFITS

Existing evidence is consistent with a very positive risk to benefit assessment. Prior clinical use of nasal steroids and the micro sponge report no adverse effects. The treatment involves only 2 applications of medication. There are no existing alternatives. Basic science studies provide evidence for promoting recovery using this drug or approach.

OBJECTIVES AND ENDPOINTS

OBJECTIVES	ENDPOINTS	JUSTIFICATION FOR ENDPOINTS
Primary		
To determine if topical intranasal treatment with beclomethasone on a micro sponge results in improved olfactory function, compared to placebo.	Olfactory function at 6 weeks and 18 weeks post-enrollment, as measured by Smell Identification Test (SIT).	SIT is a validated test for olfaction. Time points were chosen to test for early recovery of olfactory neurons versus evidence for successful regeneration, respectively.
Secondary		
To assess olfactory-specific quality of life measure in treated versus placebo groups.	Questionnaire on olfactory dysfunction (QOD) scores at 6 weeks and 18 weeks .	QOD is a validated tool for measuring quality of life related to olfactory loss.
Tertiary/Exploratory		
N/A		

STUDY DESIGN

1.8 OVERALL DESIGN

- **Hypothesis:** Treatment with topical intranasal beclomethasone on a micro sponge applied to the olfactory region of the nasal cavity will result in improved olfactory function, compared to placebo.
- **Phase 2 trial.**

- **Design:** Randomized, placebo-controlled, double-blind study.
- **Study groups:** Treatment versus Placebo.
- **Number of Sites:** Single site.
- **Study Intervention:** Beclomethasone on a microsphere

1.9 SCIENTIFIC RATIONALE FOR STUDY DESIGN

We seek to determine if treatment with Beclomethasone on a microsphere will improve olfaction in post-COVID patients with persistent olfactory loss. To obtain high quality evidence, we chose a prospective randomized placebo control double blind approach. There is no standard of care treatment or drug that can be used for comparison; the current standard of care is observation. To avoid bias, a double blind approach will be used. Based on the best knowledge for mechanism of olfactory loss in these patients, we believe that directed topical nasal delivery of an anti-inflammatory to the olfactory area of the nasal cavity is likely to be effective.

1.10 JUSTIFICATION FOR DOSE

Dose regimen is based on known pharmacology of beclomethasone and known time for microsphere to dissolve. Beclomethasone is a longer-acting topical nasal glucocorticoid drug, compared to other available choices. The microsphere is designed to elute medication for about a week. We chose a single re-application at 2 weeks to deliver a total course of treatment that covers approximately one month.

1.11 END OF STUDY DEFINITION

The end of the study is defined as completion of the last visit shown in the SoA.

STUDY POPULATION

1.12 INCLUSION CRITERIA

In order to be eligible to participate in this study, an individual must meet all of the following criteria:

1. Presents to Duke HNSCS clinic with post-COVID hyposmia lasting greater than 3 months following COVID19 by history, with olfaction documented by University of Pennsylvania Smell Identification Test (SIT).
2. Male or female, aged 18 years or older
3. Provision of signed and dated informed consent form
4. Stated willingness to comply with all study procedures and availability for the duration of the study

1.13 EXCLUSION CRITERIA

An individual who meets any of the following criteria will be excluded from participation in this study:

1. Pregnancy or lactation
2. Known allergic reactions to components of microsphere or to beclomethasone
3. Known diagnosis of glaucoma
4. Febrile illness within 1 week
5. Treatment with another investigational drug or other intervention within 3 months
6. Active sinonasal disease by nasal exam, i.e. rhinosinusitis, nasal polyps
7. Adults unable to consent
8. Prisoners, employees or subordinates
9. Individuals who are not yet adults (infants, children, teenagers). This population is excluded because the study problem is most common in adults.

1.14 LIFESTYLE CONSIDERATIONS

Not Applicable

1.15 SCREEN FAILURES

Screen failures are defined as participants who consent to participate in the clinical trial but are not subsequently randomly assigned to the study intervention or entered in the study. A minimal set of screen failure information is required to ensure transparent reporting of screen failure participants, to meet the Consolidated Standards of Reporting Trials (CONSORT) publishing requirements and to respond to queries from regulatory authorities. Minimal information includes demography, screen failure details, eligibility criteria, and any serious adverse event (SAE). Re-screening will not be performed.

1.16 STRATEGIES FOR RECRUITMENT AND RETENTION

- Target study sample size: 10 subjects in each arm, 20 subjects total. No exclusions by gender, race and ethnicity. Anticipated number to be screened in order to reach the target enrollment: 50 subjects.
- Anticipated accrual rate: 20 subjects
- Anticipated number of sites: 1
- Source of participants: outpatient. We routinely see smell loss subjects and expect to readily identify ample number of subjects, as no treatments are available.
- Types of recruitment strategies planned: Will list trial on clinicaltrials.gov, and will notify patient advocacy groups (Smell and Taste Association of North America, STANA; 5th Sense) that help advise smell loss patients on possible trials.

Specific strategies that will be used to recruit and retain historically under-represented populations in order to meet target sample size and conform with the NIH Policy on Inclusion of Women and Minorities as Participants In Research Involving Human Subjects: We will not exclude any demographic (other than children, as stated); our population in Durham County is quite diverse; the study population is anticipated to reflect this diversity.

STUDY INTERVENTION

1.17 STUDY INTERVENTION(S) ADMINISTRATION

1.17.1 STUDY INTERVENTION DESCRIPTION

Subjects will be randomized to receive either beclomethasone or placebo, to be prepared by our research pharmacy. Drug will be administered intranasally by an otolaryngologist at 2 outpatient visits, using a nasal endoscope to place the delivery microsphere in the olfactory region of the nasal cavity and then applying the drug or placebo onto the microsphere. This delivery method will direct the drug to the proper region of the nasal cavity and will prevent it from rapidly leaving this location (i.e., dripping inferiorly to the nasal floor).

Beclomethasone is available by prescription as a topical nasal spray; one brand name is Beconase AQ, GlaxoSmithKline. This is a microcrystalline suspension of beclomethasone dipropionate, monohydrate equivalent to 42 mcg of beclomethasone dipropionate, calculated on the dried basis, in an aqueous medium containing microcrystalline cellulose, carboxymethylcellulose sodium, dextrose, benzalkonium chloride, polysorbate 80, and 0.25% v/w phenylethyl alcohol.

1.17.2 DOSING AND ADMINISTRATION

Drug will be administered intranasally by an otolaryngologist at 2 outpatient visits, using a nasal endoscope to place the delivery microsphere in the olfactory region of the nasal cavity and then applying the drug or placebo onto the microsphere.

1.18 PREPARATION/HANDLING/STORAGE/ACCOUNTABILITY

1.18.1 ACQUISITION AND ACCOUNTABILITY

Randomization, drug and placebo preparation, and packaging will be done Duke research pharmacy following their established protocols for double-blind studies. When ordered, the dose will be administered by a physician otolaryngologist in outpatient clinic.

1.18.2 FORMULATION, APPEARANCE, PACKAGING, AND LABELING

Research pharmacy will prepare and label study drug or placebo appropriately for double-blind study.

1.18.3 PRODUCT STORAGE AND STABILITY

Drug is to be stored at room temperature.

1.18.4 PREPARATION

No preparation will be required. Drug or placebo will be administered ontranasally by physician at 2 visits.

1.19 MEASURES TO MINIMIZE BIAS: RANDOMIZATION AND BLINDING

To minimize bias, this will be a randomized double-blind trial. We will use the Duke Research Pharmacy to prepare study drug or placebo, using their randomization procedures and labeling. Trial randomization codes will be maintained until planned enrollment is reached and the final patient has completed the planned follow up visits. There are no planned lab studies or measures that would be expected to lead to inadvertent unblinding. If there are serious adverse events (SAEs), this will be reported to the PI and unblinding for the affected subject would be performed.

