1.22 DISCONTINUATION OF STUDY INTERVENTION

If a patient notes a possible adverse effect, such as allergic reaction to study medication, we will discontinue study medication. Any new clinically relevant finding will be reported as an adverse event (AE). Because the outpatient course of study medication is only 6 days, we will not restart study medication in that short timeframe and instead will withdraw the patient from this study. Such patients will still be offered planned follow up and the planned outcome measures will still be collected.

The data to be collected at the time of study intervention discontinuation will include the following:

- Details of possible adverse event, and appropriate care as indicated (for example ER assessment).

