1.27 ADVERSE EVENTS AND SERIOUS ADVERSE EVENTS

1.27.1 DEFINITION OF ADVERSE EVENTS (AE)

Adverse event means any untoward medical occurrence associated with the use of an intervention in humans, whether or not considered intervention-related (21 CFR 312.32 (a)).

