1.27.2 DEFINITION OF SERIOUS ADVERSE EVENTS (SAE)

An adverse event (AE) or suspected adverse reaction is considered "serious" if, in the view of either the investigator or sponsor, it results in any of the following outcomes: death, a life-threatening adverse event, inpatient hospitalization or prolongation of existing hospitalization, a persistent or significant incapacity or substantial disruption of the ability to conduct normal life functions, or a congenital anomaly/birth defect. Important medical events that may not result in death, be life-threatening, or require hospitalization may be considered serious when, based upon appropriate medical judgment, they may jeopardize the participant and may require medical or surgical intervention to prevent one of the outcomes listed in this definition. Examples of such medical events include allergic reaction requiring intensive treatment in an emergency room or at home.

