1.27.3.2 RELATIONSHIP TO STUDY INTERVENTION

All adverse events (AEs) must have their relationship to study intervention assessed by the clinician who examines and evaluates the participant based on temporal relationship and his/her clinical judgment. The degree of certainty about causality will be graded using the categories below. In a clinical trial, the study product must always be suspect.

- **Related** – The AE is known to occur with the study intervention, there is a reasonable possibility that the study intervention caused the AE, or there is a temporal relationship between the study intervention and event. Reasonable possibility means that there is evidence to suggest a causal relationship between the study intervention and the AE.
- **Not Related** – There is not a reasonable possibility that the administration of the study intervention caused the event, there is no temporal relationship between the study intervention and event onset, or an alternate etiology has been established.

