1.27.3.3 EXPECTEDNESS

PI will be responsible for determining whether an adverse event (AE) is expected or unexpected. An AE will be considered unexpected if the nature, severity, or frequency of the event is not consistent with the risk information previously described for the study intervention.

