1.27.6 SERIOUS ADVERSE EVENT REPORTING

The study clinician will immediately report to the Duke Human Subjects Research Office any serious adverse event, whether or not considered study intervention related, including those listed in the protocol or investigator brochure and must include an assessment of whether there is a reasonable possibility that the study intervention caused the event. Study endpoints that are serious adverse events (e.g., all-cause mortality) must be reported in accordance with the protocol unless there is evidence suggesting a causal relationship between the study intervention and the event (e.g., death from anaphylaxis). In that case, the investigator must immediately report the event to the sponsor.

All serious adverse events (SAEs) will be followed until satisfactory resolution or until the site investigator deems the event to be chronic or the participant is stable.

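### Section 1.19 unblinds a participant after any serious adverse event, related or not, without requiring a need or naming who learns the arm

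*Combined protocol and SAP*

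**What the plan says.** Section 1.19 (randomization and blinding) has two sentences on the codes. The first keeps them closed to the end: "Trial randomization codes will be maintained until planned enrollment is reached and the final patient has completed the planned follow up visits". The second opens them for individuals: "If there are serious adverse events (SAEs), this will be reported to the PI and unblinding for the affected subject would be performed". The second is not worded as an exception to the first. It sets no condition of relatedness, expectedness or need, and it names no recipient of the allocation.

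What counts as an SAE is set elsewhere in the protocol:

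- Section 1.27.1 defines adverse events "whether or not considered intervention-related".
- Section 1.27.2 includes "inpatient hospitalization or prolongation of existing hospitalization" among the serious outcomes, with no reference to cause.
- Section 1.27.6 requires reporting of "any serious adverse event, whether or not considered study intervention related", and the report must include a causality assessment.

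On who judges the event, section 1.27.3.2 says "All adverse events (AEs) must have their relationship to study intervention assessed by the clinician who examines and evaluates the participant", and section 1.27.3.3 says "PI will be responsible for determining whether an adverse event (AE) is expected or unexpected". Neither says whether the judgment comes before or after the code is opened.

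Section 1.23 lets an investigator withdraw a participant because of an adverse event. It replaces treated participants who are withdrawn, and it leaves anyone without the full course out of the outcome analysis.

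**The concern.** Section 1.9 relies on double blinding to avoid bias. A code break is justified when someone needs the allocation, usually to care for the participant. Section 1.19 asks for no such need: an admission for an unrelated injury would open the code just as a severe allergic reaction would.

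At stake are the judgments made about that participant once the arm is known. Some are discretionary, and one of them, withdrawal, determines who enters the outcome comparison in a trial of 10 per arm.

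**Working it through.** The plan states no figure on this point, so there is none to reproduce. The check has two parts: reading the sections together, and an illustration of how often the rule would operate.

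**1. Is the trigger really unconditional?** Section 1.19 opens the code if there is an SAE. Sections 1.27.1, 1.27.2 and 1.27.6 make SAEs include unrelated events. No other section narrows the trigger. So the rule covers every SAE in a randomized participant.

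**2. What does a code break expose, by time of the event?** The schedule in section 1.3 puts the second application at Day 14, and SIT and QOD at weeks 6 and 18.

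- *Before the second application.* The investigator may withdraw the participant (section 1.23). A participant who does not get both applications is left out of the outcome analysis, and one withdrawn after treatment is replaced. If the arm is known when that decision is made, knowledge of the arm can influence who is analysed. Section 1.31 lists only an all-randomized set, which does not fit the exclusion in section 1.23; the exposure described here follows section 1.23.
- *After the second application and before week 18.* The course is complete, so the participant stays in the analysis. On nominal days this is 18 × 7 − 14 = 112 of 126 days, or 89% of follow-up. QOD is self-reported and could be affected if the participant learns the arm. SIT is self-administered with forced-choice answers (section 1.25) and is much less exposed.
- *After the week 18 visit.* Section 1.27.4 records SAEs until 30 days after participation ends. A code break then cannot affect that participant's SIT or QOD.
- *At any time after randomization.* The PI's expectedness judgment, and any later revision of causality, could be made with the arm known.

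**3. How often would the rule operate?** Inputs: N = 20 (section 1.30) and p, the chance that a randomized participant has at least one SAE. The documents give no SAE rate, so p is assumed. With independent participants, P(at least one code break) = 1 − (1 − p)^20 and the expected number is 20p.

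| Assumed p | 1 − (1 − p)^20 | Expected number |
|---|---|---|
| 1% | 1 − 0.99^20 = 0.182 | 0.2 |
| 2% | 1 − 0.98^20 = 0.332 | 0.4 |
| 5% | 1 − 0.95^20 = 0.642 | 1.0 |

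One participant is 1/20 = 5% of the trial and 1/10 = 10% of an arm; the second figure matters only if that participant would be analysed.

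**The case against.** The strongest reply is that this is a gap in wording with little consequence. Several parts of it stand.

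- *A reader might infer that the code goes to the PI.* Section 1.19 says that the event is reported to the PI and that unblinding is performed; it does not say to whom. The PI is a natural guess because nobody else is named, but it remains a guess. The silence is itself something to correct.
- *A reader might infer that relatedness is judged with the arm known.* This does not follow. Section 1.27.6 requires an immediate report that already contains a causality assessment, and section 1.19 mentions reporting before unblinding. The likely order is causality first, although no section fixes it. What remains is later revision of causality, and expectedness. Section 1.32.4 tabulates adverse events only by number and severity, so relatedness enters no planned summary.
- *A reader might cite section 1.22 to show that outcomes are analysed after unblinding.* That section says "Such patients will still be offered planned follow up and the planned outcome measures will still be collected", but it concerns stopping for a possible adverse effect. Under section 1.23, patients whose course is incomplete as a result are left out of the outcome analysis, so their scores are collected but not compared.
- *The outcomes are robust.* This is largely true of SIT. QOD is exposed only if the participant, and not just staff, learns the arm, which the plan does not state.
- *SAEs will be rare.* Section 1.7.3 reports no adverse effects in prior use, and there are only two applications. But the rule also counts events unrelated to the product, so a clean record for the product does not settle how often it operates.

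None of this supplies a condition that section 1.19 lacks. The withdrawal route is also untouched, because it does not depend on how SIT is scored.

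**Conclusion.** The point holds in a limited form. As written, section 1.19 breaks the blind for any participant with an SAE, whatever its cause, with no need shown and no recipient named, and it sits unreconciled beside the sentence that keeps the codes closed until the end.

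The text does not support saying that the trial's double blind is lost: the break concerns one participant at a time. Nor does it support saying that every such code break would be unnecessary, since for some events the allocation may be needed for care. The defect is that need does not have to be shown.

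Three elements are exposed: the withdrawal decision before the second application, which through exclusion and replacement reaches the analysis set; the PI's expectedness judgment and any later revision of causality; and QOD in participants who have an SAE before week 18, complete both applications and learn their arm. The effect on mean SIT is probably small.

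The 18%, 33% and 64% rest on assumed SAE rates and on independence between participants. They say how often the rule might operate, not how large a bias would be. The change is worth making because it is cheap and the present rule protects nothing that a need-based rule would not.

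**What to change.** Reword section 1.19 so that:

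1. An SAE is reported to the PI with the PI still blinded, and causality and expectedness are recorded before any code is opened.
2. The research pharmacy opens an individual code only when the treating clinician states that the allocation is needed for that person's care, or when a regulator or the IRB requires it. Whether care requires the code remains the clinician's decision.
3. The allocation goes only to those who need it and, where feasible at a single site, not to those who collect SIT and QOD or run the analysis.
4. Each code break is logged with its date and reason.
5. The sentence on keeping the codes until the last visit names this as its exception.

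The cost is a wording change plus a small procedure: the clinician has to ask for the code, the site has to settle who may receive it, and a short log has to be kept. The research pharmacy already runs the randomization and labeling, so no new party is needed.
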